[Part 1 of 2 of the document. The other parts are not shown.]

## PROTOCOL AMENDMENT SUMMARY OF CHANGES TABLE

DOCUMENT HISTORY	
Document	Date
Amendment 7	This document
Amendment 6	04 September 2021
Amendment 5	07 May 2021
Amendment 4	22 February 2021
Amendment 3	14 December 2020
Amendment 2	29 October 2020
Amendment 1	15 September 2020
Original Protocol	22 July 2020

### Amendment 7 (This document)

#### Overall Rationale for the Amendment:

Following emergency use authorization (EUA) by the United States (US) Food and Drug Administration (FDA), the conditional marketing authorization by the European Commission, all participants were gradually unblinded and a single dose of Ad26.COV2.S was offered to enrolled participants who initially received placebo. Also, the epidemic continued, and new variants of concern emerged, national recommendations introduced booster vaccinations. The final analyses of the study that described the double-blind phase has been completed and the primary and secondary objectives have been met. Further efficacy evaluations of the open-label data have limitations, due to the loss of the placebo group, due to the loss of randomization, as many participants in the placebo groups in the studies did not cross over to Ad26.COV2.S (eg, they received another vaccine), and unblinding (eg, the participants' knowledge of the number and type of doses received or the timing since vaccination), which could have led to behavioral changes impacting the results. Operational challenges have impacted the feasibility of a strict follow-up of any COVID-19 episode and active follow-up cannot be sustained. Because of these reasons, the protocol has been amended to reduce the number of on-site visits and to change the requirements for COVID-19 episode reporting by applying a passive follow-up approach. Participants in the Immunogenicity Subset will continue with the on-site study visits. There are no changes to follow-up of safety endpoints, including the reporting of adverse events of special interest (AESIs). Two analyses are still planned for the study, a first analysis will be conducted for the open-label phase of the study (using the initially designed "active" follow-up of COVID-19 events) and a second end of study analysis is planned (using passive follow-up of COVID-19 events). The changes made to the clinical protocol VAC31518COV3001 as part of Protocol Amendment 7 are listed below, including the rationale of each change and a list of all applicable sections.

Section Number and Name	Description of Change	Brief Rationale

Synopsis
 
1.2 Schema
 
1.3 Schedules of Activities
 
2.1 Study Rationale
 
3 OBJECTIVES AND ENDPOINTS
 
4.1 Overall Design
 
4.4 End-of-study Definition
 
5.5 Criteria for Temporarily Delaying Administration of Study Vaccination
 
6.5 Booster Vaccination
 
6.10 Prestudy and Concomitant Therapy
 
8 STUDY ASSESSMENTS AND PROCEDURES
 
8.1.2 Procedures in the Event of (Suspected) COVID-19
 
8.1.3.4 Case Definition for Asymptomatic or Undetected COVID-19
 
8.1.3.6 Clinical Severity Adjudication Committee
 
8.2 Safety Assessments
 
8.2.1 Physical Examinations
 
8.2.2 Vital Signs
 
8.3.1 Time Period and Frequency for Collecting Adverse Event, Medically-attended Adverse Event, Adverse Events of Special Interest, and Serious Adverse Event Information
 
8.10 Assessment and Procedures Related to Booster Vaccination
 
9.2.4.2 All Participants
 
10.2 Appendix 2: Clinical Laboratory Tests
 
10.3.6 Committees Structure
 
10.4.1 Adverse Event Definitions and Classifications
 
10.7 Appendix 7: MRU Questionnaire
 
10.8 Appendix 8: Medically-attended COVID-19 (MA-COV) Form
	
The number of on-site study visits has been reduced and management of new suspected COVID-19 episodes has been changed from active to passive follow-up, defined as safety follow-up by the site at Month 18 and Month 24 to document COVID-19 participant-reported events as (S)AEs and MAAEs and to record concomitant therapies associated with COVID-19.
 
eCOA has been decommissioned.
 
No further booster doses will be provided.
	
With the cross-over vaccinations, the initial double-blind, randomized, placebo-controlled design of this study has been replaced with an open-label design, where the placebo group has been lost and received primary and booster vaccination (within or outside of the study). Finally, constant evolution of the COVID-19 pandemic has impacted the practical implementation of a strict follow-up of new suspected COVID-19 episodes.


Synopsis
 
3 OBJECTIVES AND ENDPOINTS
 
9.1 Statistical Hypotheses
 
9.7 Safety Analysis
 
9.8 Analysis of the Open-label Cross-over Phase, Open-label Booster Vaccination Phase
	
The endpoints of the open-label cross-over phase and passive follow-up phase have been added and more clarification on the open-label booster phase has been provided. The scope and endpoints of the end of study analysis have been added.
	
To more clearly differentiate between the endpoints of the open-label cross-over phase and the booster phase.
 
In addition, the changes in the follow-up of new suspected COVID-19 episodes come with endpoints specific to the follow-up phase.

10.4.3 Severity Criteria
	
Instructions were added on grading severity of thrombocytopenia AEs with platelet counts between <math>>140,000/\mu\text{L}</math> and <math><150,000/\mu\text{L}</math>.
	
Due to a discrepancy in what the FDA toxicity grading scale and the Brighton collaboration case definitions define as abnormal in terms of platelet counts.

Section Number and Name	Description of Change	Brief Rationale
Throughout the protocol	Minor errors and inconsistencies were corrected, and minor clarifications were added throughout the protocol.	Correction of minor errors and inconsistencies. Addition of minor clarifications. Alignment across sections in the protocol.

## 1. PROTOCOL SUMMARY

### 1.1. Synopsis

A Randomized, Double-blind, Placebo-controlled Phase 3 Study to Assess the Efficacy and Safety of Ad26.COV2.S for the Prevention of SARS-CoV-2-mediated COVID-19 in Adults Aged 18 Years and Older

With protocol Amendment 4, an unblinding visit was introduced at which participants who initially received placebo in the double-blind phase, and consent, receive a single dose of Ad26.COV2.S vaccine. Following the unblinding, the study is conducted in an open-label fashion.

With protocol Amendment 6, the open-label phase of the study is extended to include an open-label booster vaccination with a single dose of Ad26.COV2.S.

As of Amendment 7, the number of on-site visits for participants who are not part of the Immunogenicity Subset or Booster Subset is reduced. For these participants, any outstanding Visits 8 and 9 are cancelled. In addition, any outstanding Visits 10 and 11 are replaced by a phone call. No further booster vaccination will be provided in the protocol. In addition, active follow-up of new suspected COVID-19 will be replaced by passive surveillance (ie, follow-up by the site at Month 18 and Month 24 to document COVID-19 participant-reported events as [S]AEs and MAAEs) and to record concomitant therapies associated with COVID-19. During these calls, the protocol required safety information (eg SAEs, AESIs, MAAEs 6 month post booster) are also collected.

This study is being conducted under the sponsorship of Janssen (Janssen Vaccines & Prevention B.V) in collaboration with the COVID-19 Response Team (formerly known as Operation Warp Speed [OWS]), which also encompasses the Biomedical Advanced Research and Development Authority (BARDA), the National Institutes of Health (NIH), and the COVID-19 Prevention Trials Network (COVPN).

Ad26.COV2.S (previously known as Ad26COVS1) is a monovalent vaccine composed of a recombinant, replication-incompetent adenovirus type 26 (Ad26) vector, constructed to encode the severe acute respiratory syndrome coronavirus-2 (SARS-CoV-2) spike (S) protein.

Information about the disease, correlates of immunity, and safety issues concerning this new pandemic-causing virus are rapidly evolving. Therefore, it is critical to recognize that the approach outlined in this document might or will change as insights and discussions evolve.

## OBJECTIVES AND ENDPOINTS

### 1. Double-blind phase

The primary and secondary objectives and endpoints of the main study (ie, the double blind phase) are:

Objectives	Endpoints
Co-Primary	
To demonstrate the efficacy of Ad26.COV2.S in the prevention of molecularly confirmed a , moderate to severe/critical coronavirus disease-2019 (COVID-19) b , as compared to placebo, in SARS-CoV-2 seronegative adults	
 
First occurrence of molecularly confirmeda, moderate to severe/critical COVID-19b, with onset at least 14 days after double-blind vaccination (Day 15)
 
First occurrence of molecularly confirmeda, moderate to severe/critical COVID-19b, with onset at least 28 days after double-blind vaccination (Day 29)
 

Objectives	Endpoints
Secondaryc (The method used to perform hypothesis testing preserving the family wise error rate [FWER] will be specified in the Statistical Analysis Plan [SAP])	
Efficacy To demonstrate the efficacy of Ad26.COV2.S in the prevention of molecularly confirmed a , severe/critical COVID-19 b , as compared to placebo	
 
First occurrence of molecularly confirmeda, severe/critical COVID-19b, with onset at least 14 days after double-blind vaccination (Day 15)
 
First occurrence of molecularly confirmeda, severe/critical COVID-19b, with onset at least 28 days after double-blind vaccination (Day 29)
 

To demonstrate the efficacy of Ad26.COV2.S in the prevention of molecularly confirmed a , moderate to severe/critical COVID-19 b , as compared to placebo, in adults regardless of their serostatus	
 
First occurrence of molecularly confirmeda, moderate to severe/critical COVID-19b, with onset 1 day after double-blind vaccination
 
First occurrence of molecularly confirmeda, moderate to severe/critical COVID-19b, with onset at least 14 days after double-blind vaccination (Day 15)
 
First occurrence of molecularly confirmeda, moderate to severe/critical COVID-19b, with onset at least 28 days after double-blind vaccination (Day 29)
 

To evaluate the efficacy of Ad26.COV2.S in the prevention of molecularly confirmed a moderate to severe/critical COVID-19 b as compared to placebo, with onset 1 day after study vaccination	First occurrence of molecularly confirmed a , moderate to severe/critical COVID-19 b with onset 1 day after double-blind vaccination
To assess the effect of Ad26.COV2.S on COVID-19 requiring medical intervention (based on objective criteria) compared to placebo	
 
First occurrence of COVID-19 requiring medical intervention (such as a composite endpoint of hospitalization, ICU admission, mechanical ventilation, and ECMO, linked to objective measures such as decreased oxygenation, X-ray or CT findings) and linked to any molecularly confirmeda, COVID-19b,c at least 14 days after double-blind vaccination (Day 15)
 
First occurrence of COVID-19 requiring medical intervention and linked to any molecularly confirmeda, COVID-19b,c at least 28 days after double-blind vaccination (Day 29)
 

To assess the effect of Ad26.COV2.S on SARS-CoV-2 viral ribonucleic acid (RNA) load compared to placebo for moderate to severe/critical COVID-19 b	Assessment of the SARS-CoV-2 viral load by quantitative reverse-transcriptase polymerase chain reaction (RT-PCR), in participants with molecularly confirmed a , moderate to severe/critical COVID-19 b by serial viral load measurements during the course of a COVID-19 episode
To assess the effect of Ad26.COV2.S on molecularly confirmed a mild COVID-19 c	
 
First occurrence of molecularly confirmeda, mild COVID-19c, at least 14 days after double-blind vaccination (Day 15)
 
First occurrence of molecularly confirmeda, mild COVID-19c, at least 28 days after double-blind vaccination (Day 29)
 

Objectives	Endpoints
To assess the effect of Ad26.COV2.S on COVID-19 as defined by the United States (US) Food and Drug Administration (FDA) harmonized case definition d	
 
First occurrence of molecularly confirmeda COVID-19d at least 14 days after double-blind vaccination (Day 15)
 
First occurrence of molecularly confirmeda COVID-19d at least 28 days after double-blind vaccination (Day 29)
 

To assess the effect of Ad26.COV2.S on all molecularly confirmed a symptomatic COVID-19 b,c , as compared to placebo	
 
Burden of disease (BOD) endpointf derived from the first occurrence of molecularly confirmeda symptomatic COVID-19b,c (meeting the mild, moderate or severe/critical COVID-19 case definition) with onset at least 14 days after double-blind vaccination (Day 15).
 
BOD endpointf derived from the first occurrence of molecularly confirmeda symptomatic COVID-19b,c (meeting the mild, moderate or severe/critical COVID-19 case definition) with onset at least 28 days after double-blind vaccination (Day 29).
 

To assess the effect of Ad26.COV2.S on occurrence of confirmed asymptomatic or undetected infections with SARS-CoV-2, as compared to placebo	
 
Serologic conversions: between baseline (Day 1; pre-vaccination) and Day 29, between Day 29 and Day 71, between Day 71 and Month 6 /Unblinding Visit, and Month 18 after double-blind vaccination (approximately 12 months after initiation of the open-label phase of the study) using an enzyme-linked immunosorbent assay (ELISA) and/or SARS-CoV-2 immunoglobulin assay that is dependent on the SARS-CoV-2 nucleocapsid (N) protein
 
Asymptomatic infection detected by RT-PCR at the time of the Month 6 /Unblinding Visit
 

To assess the efficacy of Ad26.COV2.S in the prevention of SARS-CoV-2 infection (both symptomatic and asymptomatic infections combined, that are serologically and/or molecularly confirmed a ), as compared to placebo	First occurrence of SARS-CoV-2 infection (serologically and/or molecularly confirmed a ) with onset at least 28 days after double-blind vaccination (Day 29)
Safety	
To evaluate safety in terms of serious adverse events (SAEs) adverse events of special interest (AESIs) (during the entire study), medically-attended adverse events (MAAEs; until 6 months after double-blind or open-label vaccination), and MAAEs leading to study discontinuation (during the entire study) for all participants	Occurrence and relationship of SAEs and AESIs (during the entire study), MAAEs (until 6 months after [double-blind or open-label] Ad26.COV2.S), and MAAEs leading to study discontinuation (during the entire study) for all participants following vaccination
In a subset of participants, to evaluate the safety and reactogenicity in terms of solicited local and systemic adverse events (AEs) during 7 days after double-blind vaccination, and in terms of unsolicited AEs during 28 days after double-blind vaccination	Occurrence, intensity, duration, and relationship of solicited local and systemic AEs during the 7 days following vaccination and of unsolicited AEs during the 28 days after double-blind vaccination

Objectives	Endpoints
Immunogenicity	
In a subset of participants, to evaluate the immunogenicity of Ad26.COV2.S, as compared to placebo	Analysis of antibodies binding to the SARS-CoV-2 S protein by ELISA

a Molecularly confirmed COVID-19 is defined as a positive SARS-CoV-2 viral RNA result by a central laboratory using a RT-PCR based or other molecular diagnostic test.

b Per case definition for moderate to severe/critical COVID-19 as determined by the Clinical Severity Adjudication Committee (see below).

c Per case definition for mild COVID-19 as determined by the Clinical Severity Adjudication Committee (see below).

d Per US FDA harmonized case definition for COVID-19 (see below).

e All secondary efficacy endpoint analyses will occur in the per-protocol (PP) analysis set, in seronegative participants unless otherwise indicated in the Statistical Analysis Plan (SAP).

f For more information and the definition of the BOD endpoint, refer to the body of the protocol.

Exploratory objectives and endpoints, including correlates of protection, durability of protection, immunogenicity, and evaluation of efficacy in seropositive participants and/or participants with a SARS-CoV-2 positive RT-PCR or molecular test result, are included in the body of this protocol.

## Hypotheses

The study is designed to test the co-primary hypotheses of vaccine efficacy (VE) in the PP population. For both co-primary endpoints, the following hypothesis will be tested:

H0: VE  $\leq$ 30% versus H1: VE >30% and each hypothesis will be evaluated at a 2.5% one-sided significance level.

[figure not shown]
The co-primary endpoints will evaluate

- the first occurrence of molecularly confirmed, moderate to severe/critical COVID-19 according to the case definition, with onset at least 14 days after double-blind vaccination with Ad26.COV2.S versus placebo, in the PP population, including all events from both age groups, with and without comorbidities.
- the first occurrence of molecularly confirmed, moderate to severe/critical COVID-19 according to the case definition, with onset at least 28 days after double-blind vaccination with Ad26.COV2.S versus placebo, in the PP population, including all events from both age groups, with and without comorbidities.

If testing for both primary endpoint hypotheses is successful, secondary objectives will be evaluated against a null hypothesis employing a lower limit VE>0%. The method to perform hypothesis testing of primary and secondary objectives preserving the FWER will be specified in the SAP. The FWER will be controlled at 2.5% one-sided significance level.

## 2. Open-label active phase

A diagram showing the study phases is provided below:

### 2.1 Open-label Cross-over Phase

Participant will enter the open-label crossover phase on the day that the participant received the cross-over vaccination or is unblinded until the day that the participant completed the booster visit. There are 2 main cohorts in the open-label phase:

- Early vaccinated cohort: participants who were initially randomized to the Ad26.COVID2.S group and received 1 dose of Ad26.COVID2.S at Day 1 in the trial
- Late vaccinated cohort: participants who were initially randomized to the placebo group and who received 1 dose of Ad26.COVID2.S after unblinding

The main objective of the open-label phase of the study is to evaluate the COVID-19 outcomes after an early vaccination and after a late vaccination. Efficacy evaluations may be performed if feasible, ie, if pre-specified criteria are met, as specified in the SAP.

The secondary and exploratory objectives and endpoints for the open-label phase of the study are:

Objectives	Endpoints
The secondary safety objective of the double-blind phase (see secondary double-blind objective)	The secondary safety endpoint of the double-blind phase (see secondary double-blind endpoint)
To evaluate molecularly confirmed a , symptomatic COVID-19 b	Incidence of symptomatic COVID-19 cases starting at 28 days after last vaccination
To evaluate molecularly confirmed a , severe/critical COVID-19 b	Incidence of severe/critical COVID-19 cases starting at 28 days after last vaccination
To evaluate molecularly confirmed a COVID-19 b requiring medical intervention (based on objective criteria)	Incidence of COVID-19 cases requiring medical intervention, starting at 28 days after last vaccination
To evaluate COVID-19 related death	Incidence of COVID-19 related deaths starting at 28 days after last vaccination

Objectives	Endpoints
To describe the severity of breakthrough infections	The severity of COVID-19 cases may be evaluated by the severity and number of symptoms (severity) of COVID-19 cases, ratio of severe/critical COVID-19 cases and ratio of long COVID-19 cases (duration of more than 28 days)
To estimate potential correlate of risk/efficacy in relation to the primary endpoint of the main study and serious disease, hospitalization, and death based on immune responses in breakthrough cases compared to non-infected participants.	Levels of immune responses (antibody titers) and RNA sequencing analysis as available for participants having COVID-19 compared to non-infected participants.

a Molecularly confirmed COVID-19 is defined as a positive SARS-CoV-2 viral RNA result by a central laboratory using a RT-PCR based or other molecular diagnostic test.

b Per case definition for moderate to severe/critical COVID-19 as determined by the Clinical Severity Adjudication Committee (see below).

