To assess the safety and reactogenicity of Ad26.COV2.S at the $5 \times 10^{10}$ vp dose level administered as homologous or heterologous booster vaccination in adults.	
 
Solicited local and systemic AEs for 7 days after booster vaccination.
 
Unsolicited AEs for 28 days after booster vaccination.
 
SAEs and AESIs from booster vaccination until end of the study.
 

To measure the primary endpoints previously utilized for the double-blind portion of the study in this unblinded booster portion of the trial during the time participants have and have not been boosted.	
 
Incidence of the primary endpoints utilized in the double-blind portion of the study, including moderate to severe/critical COVID-19 cases starting at 28 days by serostatus*, in the unblinded booster portion of the study (see definitions of terms in Section 10.1) during the times when they have and have not been boosted.
 

To measure the primary endpoints previously utilized for the double-blind portion of the study in participants infected with selected variants and the reference strain in this unblinded booster portion of the trial during the time participants have and have not been boosted.	
 
Incidence of the primary endpoints (Day 28 after vaccination) in the main study as applicable as described in the first objective but for variants of concern and the reference strain.
 

Secondary Objectives of the Booster Phase	
To evaluate the secondary endpoints previously utilized for the double-blind portion of the study in this unblinded booster portion of the trial during the time participants have and have not been boosted.	
 
Incidence of secondary endpoints (Day 28 after vaccination) from the double-blind portion of the study by serostatus* such as symptomatic severe/critical disease, hospitalization, and death.
 

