In parallel to Stage 1a, in Stage 2 of the study, approximately 2,000 adults  $\geq 60$  years of age without comorbidities that are associated with increased risk of progression to severe COVID-19 will be enrolled (Stage 2a; including approximately 1,000 Ad26.COV2.S recipients and approximately 1,000 placebo recipients). Following enrollment of these initial 2,000 participants in Stage 2a, further vaccination in Stage 2 of the study will be paused to allow the DSMB to examine Day 3 safety data (ie, from Day 1 to Day 3; including safety data from Stage 1 and the ongoing clinical studies). Upon confirmation that there are no safety concerns in this population or in the Stage 1 population up to that point, enrollment will proceed, including participants aged  $\geq 60$  years with and without comorbidities that are associated with increased risk of progression to severe COVID-19 (Stage 2b) (see Section 1.2 [Figure 1] for a schematic overview of the study and Section 5.2 for the list of relevant comorbidities).

The total sample size for the study (including  $\geq 18$ - to  $< 60$ -year-old and  $\geq 60$ -year-old participants, and participants with and without comorbidities that are associated with increased risk of progression to severe COVID-19) will be approximately 40,000 participants. It is intended that a minimum of approximately 30% of recruited participants will be  $\geq 60$  years of age and approximately 20% of recruited participants will be  $\geq 18$  to  $< 40$  years of age.

Refer to Section 9.2.1 for details about the sample size determination.

Following EUA, conditional licensure, or approval in any country, a single dose of Ad26.COV2.S will be offered to enrolled participants who initially received placebo, where Amendment 4 is approved by the local Health Authority and IEC/IRB, resulting in de facto unblinding of participants and investigators. Of note, after the primary analysis, sponsor personnel except individuals directly in contact with study investigators are already unblinded according to the study protocol. All participants will be encouraged to remain in the study and continue to be followed for efficacy/effectiveness, safety and immunogenicity as originally planned up to 2 years after double-blind vaccination. This will allow assessment of the duration of protection and immunogenicity of a single dose of Ad26.COV2.S by comparing 2 groups vaccinated approximately 4 to 6 months apart.

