### 5.5. Criteria for Temporarily Delaying Administration of Study Vaccination

The following events constitute a temporary contraindication to study vaccination:

- Clinically significant acute illness at the time of vaccination. This does not include minor illnesses, such as diarrhea or mild upper respiratory tract infection.
- Fever (body temperature  $\geq 38.0^{\circ}\text{C}/100.4^{\circ}\text{F}$ ) within 24 hours prior to the planned time of vaccination.
- An illness which in the judgement of the investigator may interfere with reactogenicity/Day 0-7 safety assessments.

If, at the start of the double-blind phase, any of these events occur at the scheduled time for the vaccination, randomization at a later date within the screening window is permitted at the discretion of the investigator and after consultation with the sponsor. If randomization cannot occur within the screening window, rescreening is required.

If, at the start of the open-label phase, any of the above listed events occur at the scheduled time for the vaccination, the Month 6/Unblinding Visit with active vaccine can be delayed up to 28 days

following unblinding. In addition, a urine pregnancy test (for participants of childbearing potential, according to the local guidelines) will be required for the Month 6/Unblinding Visit for participants who will be vaccinated at this visit. Participants who are pregnant at the Month 6/Unblinding Visit and received placebo during the double-blind phase may be vaccinated with Ad26.COV2.S, if allowed by local regulations, and if the investigator considers that the potential benefits outweigh the potential risks to the mother and fetus (See Section 6.4).

If any of the above listed events occur at the scheduled time for the booster vaccination, the Year 1/Booster Visit with active vaccine can be delayed within the preferred visit window, but not occur later than May 15, 2022. In addition, a urine pregnancy test (for participants of childbearing potential, according to the local guidelines) will be required for the Year 1/Booster Visit for participants who will be vaccinated at this visit. Participants who are pregnant at the Year 1/Booster Visit may receive booster vaccination with Ad26.COV2.S, if allowed by local regulations, and if the investigator considers that the potential benefits outweigh the potential risks to the mother and fetus (see Section 6.5).

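### In the open-label cross-over phase, early-cohort cases count from unblinding but late-cohort cases only from 28 or more days later, so the two rates can differ without waning when incidence changes

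*Protocol*

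**What the plan says.** **Phase entry.** The Synopsis, under 2.1 Open-label Cross-over Phase, states: "Participant will enter the open-label crossover phase on the day that the participant received the cross-over vaccination or is unblinded". The phase ends when the booster visit is completed. Section 3.2.1 repeats this.

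**Cohorts.** Early-cohort participants "received 1 dose of Ad26.COVID2.S at Day 1 in the trial". The late cohort is "participants who were initially randomized to the placebo group and who received 1 dose of Ad26.COVID2.S after unblinding".

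**Endpoint.** The symptomatic endpoint is "Incidence of symptomatic COVID-19 cases starting at 28 days after last vaccination". The endpoints for severe/critical disease, cases requiring medical intervention and COVID-19 death use the same starting rule.

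**Timing.** The Schedule of Activities (Section 1.3.3) places the unblinding visit after the Day 71 visit. Section 5.5 adds that, in case of acute illness or fever, "the Month 6/Unblinding Visit with active vaccine can be delayed up to 28 days" after unblinding.

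**Purpose.** Section 2.1, Study Rationale, expects to assess duration of protection by "comparing 2 groups vaccinated approximately 4 to 6 months apart".

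**Booster phase.** One primary endpoint is phrased as "including moderate to severe/critical COVID-19 cases starting at 28 days by serostatus". The Synopsis (2.2) and Section 3.2.2 start this phase at each participant's booster visit. Overall Design (Synopsis and Section 4.1) also ties its start to the first cross-over unblinding visit.

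**The concern.** One rule, 28 days after the last dose, gives the two cohorts different starting points. For the early cohort the condition is already met at phase entry and removes nothing. For the late cohort it removes the first 28 days or more. The early rate therefore contains a stretch of the epidemic, straight after unblinding, that the late rate lacks.

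Early versus late incidence is what the protocol offers as evidence on durability once the placebo group is gone. If the epidemic is receding after unblinding, the early cohort looks worse and the difference can be read as waning. If it is growing, real waning can be hidden. Section 2.1 itself says that the epidemic continued and new variants emerged, so constant incidence is not a safe assumption.

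**Working it through.** The plan states no figure for this contrast, so there is none to reproduce. The check derives the counting windows and then the rate ratio when both cohorts have identical hazards.

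**Inputs from the protocol**
- Nominal unblinding visit: Week 24 = day 168. The preferred window is read as 106 days before to 28 days after (the minus sign is lost in the text), so day 62 to day 196.
- Nominal booster visit: Week 52 = day 364. The preferred window is read as 100 days before to 170 days after, so day 264 to day 534.
- Deferral of the cross-over dose: 0 to 28 days.

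**Step 1: counting start = later of (phase entry, last dose + 28 days)**
- Early cohort: Day 1 dose + 28 days has passed even at the earliest preferred unblinding (62 − 28 = 34 days to spare). Counting starts at unblinding.
- Late cohort: cross-over dose + 28 days, which is 28 to 28 + 28 = 56 days after unblinding.
- Both end at the booster visit.

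**Step 2: overlap**

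Nominal phase length L = 364 − 168 = 196 days. With offset d = 28, the late window covers 168 of 196 days (86%), all of it inside the early window. Only the first 28 days are unmatched.

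**Step 3: ratio with no waning**

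Assume incidence in the first d days is r times the later level. Then early/late = (d·r + L − d)/L.

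| r (assumed) | d = 28, L = 196 | Ratio |
|---|---|---|
| 0.5 | (14 + 168)/196 | 0.93 |
| 1 | (28 + 168)/196 | 1.00 |
| 2 | (56 + 168)/196 | 1.14 |
| 4 | (112 + 168)/196 | 1.43 |

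Phase length matters. The shortest from the preferred windows is 264 − 196 = 68 days, giving 1.41 (r = 2) and 2.24 (r = 4). The longest is 534 − 62 = 472 days, giving 1.06 and 1.18.

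**Step 4: smooth trend instead of a step**

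With incidence proportional to exp(kt), the ratio is [(e^{kL} − 1)/(kL)] ÷ [(e^{kL} − e^{kd})/(k(L − d))]. For L = 196 and d = 28, halving every 56 days gives 1.26 and doubling every 56 days gives 0.89.

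**Step 5: bound for deferral**

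If every late participant were deferred the full 28 days (d = 56) and incidence were raised throughout those 56 days, r = 2 gives (112 + 140)/196 = 1.29 and r = 4 gives (224 + 140)/196 = 1.86. This is an outer bound.

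**Step 6: yardstick (assumed)**

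True waning of vaccine efficacy from 70% to 60% gives (1 − 0.60)/(1 − 0.70) = 1.33.

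**Step 7: after alignment**

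If both cohorts start on the same day, identical hazards give 1.00 for any incidence curve.

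A separate point: if incidence is reported as a cumulative proportion and not a rate, the longer window alone gives about 196/168 = 1.17 at constant hazard.

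**The case against.** **Left to the SAP.** Open-label populations and analytic details are deferred to the SAP, and person-time rules are usually settled there. But the counting rule is written into the protocol endpoint, so this is a stated rule and not an omission. The early cohort's start at unblinding is inferred from phase entry. If counting ran from 28 days after Day 1 regardless of phase, the mismatch would be larger.

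**Descriptive, and already hedged.** The protocol plans to summarize these endpoints descriptively, Section 3.2.1 calls the objectives exploratory, and the protocol acknowledges lost randomization, outside vaccination and behavioral change. This stands and limits the weight of the point. The offset is nevertheless not among the listed limitations, and unlike them it can be avoided.

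**Staggered unblinding.** Participants' first 28 days do not coincide in calendar time, so one common multiplier is a simplification. This stands for a short wave. It does not remove the effect of a sustained trend, because each late participant still starts 28 or more days after unblinding.

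**Stronger readings that the protocol does not support**
- A reader might infer that the rates cover separate periods or must differ. The late window is nested in the early one, and the ratio is exactly 1 at constant incidence.
- A reader might infer that no epidemic adjustment is planned for early versus late. The Synopsis says adjustment for variants and the epidemic will be explored, in text that follows the booster comparison. Its scope is arguable, and Section 9.8, which covers these analyses, was not available for this review.
- A reader might carry the same 28-day bias over to boosted versus non-boosted time. That depends on which phase-start definition applies. Non-boosted participants stay in their cohort until boosted, and data from before boosting may be used.
- A reader might treat 56 days as the typical offset. It applies only to participants whose dose is deferred to the limit.

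**Conclusion.** The point holds for the cross-over phase. The phase-entry rule and the 28-day rule together give the early cohort at least 28 more days of counted time at the start. Without waning, the early/late rate ratio in the nominal 196-day phase is 1.00 at constant incidence, 1.14 or 1.43 if incidence in the first 28 days is 2 or 4 times the later level, and 0.93 if it is half. The upper end exceeds the 1.33 that a fall in efficacy from 70% to 60% would give.

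These sizes rest on assumed incidence patterns, so neither direction nor magnitude can be fixed from the protocol. They also assume that person-time starts with case counting. For the booster phase the supported conclusion is narrower: its start is defined in two ways, and the calendar-time adjustment mentioned is only to be explored. The change should be made, but nothing here touches the double-blind primary analysis.

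**What to change.** **Cross-over phase (Synopsis 2.1 and Section 3.2.1).** For the early-versus-late comparison, either:
- count cases and person-time in both cohorts from a common start, 28 days after the unblinding visit or cross-over dose, with the same lag given to early-cohort participants (where the dose was deferred, for example those of the same site and week); or
- compare rates within calendar-time strata by country.

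State that incidence is per person-time.

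**Booster phase.** Reconcile the start definition in Synopsis 2.2 and Section 3.2.2 with that in Overall Design (Synopsis and Section 4.1). Commit to the calendar-time stratification that the Synopsis now only proposes to explore.

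**Cost.** Endpoint wording and the matching derivation; no new data. A common start removes about 28/196 = 14% of early-cohort person-time from the comparison, and that time can be shown separately. Stratification keeps it, but early-cohort time in strata without late-cohort time adds nothing to the contrast.
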